6.3 PACKAGING AND LABELING

Packaging and labeling will be prepared to meet regulatory requirements. Package integrity and labelling should be verified prior to use of the product.

6.3.1 Labeling of Investigational Product

The REGENETEN Bioinductive Implant System is an investigational product in China. Addition labels will be included on the commercial packaging to specify that the product is for clinical trial use only in order to meet regulatory requirements for use of investigational devices.

In the United States, Singapore, Hong Kong, Europe, Canada, Australia and New Zealand, the REGENETEN Bioinductive Implant System is a commercial product and will be used as cleared/licensed. Product labeling will be the same as per standard commercial packaging.

In Japan, the REGENETEN Bioinductive Implant System is a product that will be cleared/registered before study enrollment. The product will only be used either through market approval and/or special access approval.

For China only, labels on the REGENETEN Bioinductive Implant System contain the following information in addition to standard commercial packaging:

- Study number,
- Clinical Investigation Use Only.

Any regulatory status updates that may impact labeling requirements moving forward will be managed via TMP-CD-18-01 Investigational Products/Ancillary Products/Supplies Protocol.

CONFIDENTIAL AND PROPRIETARY

Study Protocol	Smith-Nephew
A Prospective, Multi-center, Randomized Controlled	Number:
Study to Evaluate the Safety and Efficacy of ARCR	REGENETEN.2020.01
augmented with REGENETEN™ Bioinductive Implant	Version: 2, 08 Dec 2021
System in Full-thickness Tears (large or massive) Repair versus ARCR alone	Page: 35 of 134

6.4 PRODUCT ACCOUNTABILITY PROCEDURES

This study is a post-market study in Unites States, Singapore and Hong Kong and the products will only be used when cleared/registered in Australia, New Zealand, Europe and Canada. However, the sponsor provides the study sites with the REGENETEN System. Therefore, a site level accountability log will be completed for all supplied products at each study site for compliance. The investigational site will maintain an inventory of the Investigational Device. The Sponsor or its designee will provide a log(s) to facilitate Investigational Device inventory control. The log will contain details of receipt, use, returns etc. of Investigational Devices. All Investigational Device accountability logs must be retained in the Investigator Site File (ISF). These records must be available for inspection by the Sponsor, its designees, or by regulatory agencies at any time. Investigational Device Management Instructions will be provided by the Sponsor to the site detailing all additional forms that might need completion (e.g., confirmation of receipt) for Investigational Device control.

The study monitor will ensure that the procedures and records are in place for the appropriate reconciliation of all Investigational Devices. As part of monitoring, the study monitor will check that site personnel are following the proper procedures for accountability and completing all necessary documentation.

6.5 SURGICAL TECHNIQUE

The REGENETEN System should be used according to the surgical technique and IFUs provided with the investigational device per Section 6.1.1.1

Investigators participating in this study must be proficient in arthroscopic rotator cuff repairs.

In addition, prior to implantation of the REGENETEN System, all principal surgical investigators involved in the REGENETEN procedure must be trained with respect to surgical technique, use of the device and surgical approach, so as to ensure consistency in the implementation of the clinical trial protocol and the use of the investigational device. Investigators must go through all

CONFIDENTIAL AND PROPRIETARY

Study Protocol	Smith-Nephew
A Prospective, Multi-center, Randomized Controlled	Number:
Study to Evaluate the Safety and Efficacy of ARCR	REGENETEN.2020.01
augmented with REGENETEN™ Bioinductive Implant	Version: 2, 08 Dec 2021
System in Full-thickness Tears (large or massive) Repair versus ARCR alone	Page: 36 of 134

steps of procedure at least once, using all provided instruments on a test case, either in Arthroscopy Wet Lab or similar environment or real patient before enrollment.

CONFIDENTIAL AND PROPRIETARY

Study Protocol	Smith-Nephew
A Prospective, Multi-center, Randomized Controlled	Number:
Study to Evaluate the Safety and Efficacy of ARCR	REGENETEN.2020.01
augmented with REGENETEN™ Bioinductive Implant	Version: 2, 08 Dec 2021
System in Full-thickness Tears (large or massive) Repair versus ARCR alone	Page: 37 of 134

7. SUBJECT ENROLLMENT AND WITHDRAWAL

7.1 SUBJECT POPULATION

Up to 300 subjects will be enrolled into the study in up to 30 sites in the United States, Canada, United Kingdom, France, Switzerland, Germany, China, Singapore, Hong Kong, Australia and New Zealand, Japan and Netherlands:

- 130 ARCR augmented with REGENETEN;
- 130 ARCR alone:
- Up to 40 revision repair subjects will be recruited into one additional single group (ARCR supplemented with REGENETEN in recurrent tears (full-thickness tears [large or massive]).

Subjects selected for this clinical trial are in need of full-thickness rotator cuff tear repair or revision repair (for revision repair subject group only).

7.2 INCLUSION CRITERIA

Subjects will be considered qualified for enrollment if they meet the following criteria:

- 1. Subject requires Arthroscopic rotator cuff repair (ARCR).
- 2. Subjects with a diagnosis of a symptomatic primary or recurrent (revision repair subject group), large or massive tear (≥ 3 cm AP/ML) of the supraspinatus and/or infraspinatus tendons amenable to repair. For screening purposes, a ≥ 2 cm AP/ML tear as measured on MRI will be eligible to proceed to the operative visit but will have to be confirmed as ≥ 3 cm on arthroscopy using a calibrated probe to proceed.
- 3. Subject is > 40 years of age (no upper limit).
- 4. Subject provides written informed consent for study participation using an Independent Ethical Committee (IEC) / Institutional Review Board (IRB) approved consent form.

CONFIDENTIAL AND PROPRIETARY

Study Protocol	Smith-Nephew
A Prospective, Multi-center, Randomized Controlled	Number:
Study to Evaluate the Safety and Efficacy of ARCR	REGENETEN.2020.01
augmented with REGENETEN™ Bioinductive Implant	Version: 2, 08 Dec 2021
System in Full-thickness Tears (large or massive) Repair versus ARCR alone	Page: 38 of 134

5. Subject is willing and able to participate in required follow-up visits and is able to complete study activities.

7.3 EXCLUSION CRITERIA

Any of the following criteria will disqualify a potential subject from participation in the study:

- 1. Subjects who are unable to tolerate magnetic resonance imaging (MRI), due to psychiatric or medical contraindications.
- 2. Subjects with Samilson-Prieto osteoarthritis > 2.
- 3. Subjects with current or prior infection of the ipsilateral shoulder.
- 4. Subjects with known hypersensitivity to bovine-derived materials.
- 5. Subjects with known inflammatory arthropathy, history of inflammatory arthropathy, or chronic joint disease.
- 6. Subjects with prior shoulder surgery (not including rotator cuff repair [revision repair subject group only], biceps tenodesis/tenotomy, distal clavicle excision [DCE], subacromial decompression).
- 7. Subjects with an irreparable or partially reparable rotator cuff tear.
- 8. Subjects with a subscapularis tear requiring repair.
- 9. Subjects requiring a concomitant labral fixation procedure.
- 10. Subjects requiring a concomitant os acromiale fixation procedure.
- 11. Subjects with glenohumeral joint instability (multiple dislocations/subluxations).
- 12. Subjects with a subacromial or intra-articular injection within 3 months prior to surgery.

CONFIDENTIAL AND PROPRIETARY

Study Protocol	Smith-Nephew
A Prospective, Multi-center, Randomized Controlled	Number:
Study to Evaluate the Safety and Efficacy of ARCR	REGENETEN.2020.01
augmented with REGENETEN™ Bioinductive Implant	Version: 2, 08 Dec 2021
System in Full-thickness Tears (large or massive) Repair versus ARCR alone	Page: 39 of 134

- 13. Subjects with condition(s) that contraindicate or complicate outcome of ARCR e.g., > Hamada 3 rotator cuff arthropathy on X-ray, Goutallier atrophy > Grade 3, proximal humeral fracture or scapular fracture, avascular necrosis of the humeral head or glenoid, history of immunodeficiency disorders, history of chronic inflammatory disorders, oral or injected steroid use in last 4 weeks.
- 14. Subjects who are pregnant or breast feeding.
- 15. Subjects who are currently involved in any litigation or workers compensation claims.
- 16. Subjects who are enrolled, or plan to enroll, in another clinical trial during this study that would affect the outcomes of this study.
- 17. Subjects with a history of noncompliance with medical treatment, PT/rehabilitation, or clinical study participation.
- 18. Subject who, in the opinion of the Investigator, has an emotional or neurological condition that would pre-empt their ability or willingness to participate in the study including mental illness, mental retardation, and drug or alcohol abuse.
- 19. Subjects who do not meet the indication or are contraindicated according to specific Smith+Nephew REGENETEN System's IFUs.
- 20. Subject that meets the definition of a Vulnerable Subject per ISO14155:2020 Section 3.44.

7.4 SCREENING

The Investigators will continuously screen subjects during recruitment, which will continue until a total of up to 300 subjects (130 ACRC augmented with REGENETEN, 130 ARCR alone and up to 40 revision repair subjects) are recruited. It remains the decision of the Sponsor to increase or decrease enrollment, as necessary.

Once a subject has completed the informed consent procedure and signed the Informed Consent Form (IFU), the Principal Investigator (PI), or delegated study research staff, can complete the

CONFIDENTIAL AND PROPRIETARY

Study Protocol	Smith-Nephew
A Prospective, Multi-center, Randomized Controlled	Number:
Study to Evaluate the Safety and Efficacy of ARCR	REGENETEN.2020.01
augmented with REGENETEN™ Bioinductive Implant	Version: 2, 08 Dec 2021
System in Full-thickness Tears (large or massive) Repair versus ARCR alone	Page: 40 of 134

screening process to determine whether they meet all inclusion and none of the exclusion criteria. This might be the same day or another day, giving the subject enough time to consider participation.

Participating study sites are required to document all screened subjects considered for inclusion in this study on a Screening and Enrollment Log. If a subject is excluded from the study, the reasons for exclusion will be noted on the Screening and Enrollment Log.

In the event that a subject has the need for sequential bilateral ARCR augmented with REGENETEN or standard arthroscopic rotator cuff repair (ARCR), both shoulders may be enrolled in the study after informed consent process. Post-operative physical standard of care therapy guidelines and restrictions as stated in section 6.2 Product Use should be maintained for best outcome.

In the event that operation is delayed and outside Screening Visit Day time window, screening process has to be repeated to confirm eligibility.

7.5 INFORMED CONSENT

Before conducting any study related procedures, informed consent shall be obtained from all participating subjects according to ISO14155:2020 guidelines or applicable NMPA requirements in China. This can be done on the same day as the screening eligibility confirmation or another day giving the subject enough time to consider participation. Investigators are responsible for obtaining and documenting the voluntary informed consent as well as obtaining the IRB/EC approval for the Informed Consent Form (ICF) and any other written information provided to the subject.

The ICF and any other written information provided to subjects should be revised whenever important new information becomes available that may be relevant to the subject's continued consent. All revised ICFs must have written and dated IRB/EC approval prior to use.

CONFIDENTIAL AND PROPRIETARY

Study Protocol	Smith-Nephew
A Prospective, Multi-center, Randomized Controlled	Number:
Study to Evaluate the Safety and Efficacy of ARCR	REGENETEN.2020.01
augmented with REGENETEN™ Bioinductive Implant	Version: 2, 08 Dec 2021
System in Full-thickness Tears (large or massive) Repair versus ARCR alone	Page: 41 of 134

The purpose and nature of the study and the potential risks and benefits known as described in the written ICF should be explained to the subject in their native language.

The subject will have sufficient opportunity to consider participation in the study. The subject, will read, sign, and personally date the IRB/EC-approved informed consent document(s), indicating their consent for enrollment. Additionally, the individual who obtains consent from the subject will sign and date the informed consent document. The communications with the subject regarding informed consent process (initial and subsequent) will be documented in the medical record. Subjects should receive a copy of the initial signed and dated ICF (in their native language) and any revised ICFs during the study.

ICFs will comply with Health Information Portability Accountability Act (HIPAA) regulations the EU Global Data Protection Regulation (GDPR), The Privacy Act 1988 in Australia and the New Zealand Privacy Act 1993 and or applicable national regulations and laws.

7.6 ENROLLMENT

Every subject that has signed consent, met inclusion/exclusion criteria, and received either ARCR augmented with REGENETEN or ARCR alone will be considered enrolled in the study.

In the event that a subject has a sequential bilateral ARCR augmented with REGENETEN or ARCR alone, both shoulders treated after informed consent can be enrolled in the study.

A subject that has been randomized into the ARCR augmented with REGENETEN arm and with a diagnosis of a recurrent large or massive tear will not be enrolled into the revision repair subject group. However subjects that were randomized into the ARCR alone arm can be enrolled into the revision repair subject group in case of recurrent large or massive tears.

Subjects that provided informed consent but do not receive the study treatment for any reason will be considered as screen failure.

CONFIDENTIAL AND PROPRIETARY

Study Protocol	Smith-Nephew
A Prospective, Multi-center, Randomized Controlled	Number:
Study to Evaluate the Safety and Efficacy of ARCR	REGENETEN.2020.01
augmented with REGENETEN™ Bioinductive Implant	Version: 2, 08 Dec 2021
System in Full-thickness Tears (large or massive) Repair versus ARCR alone	Page: 42 of 134

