7.8 WITHDRAWAL

7.8.1 Withdrawal from Treatment

Subjects may be withdrawn from having the study device implanted at a date close to surgery or during surgery for the following reasons:

- At the discretion of the Investigator due to:
 - A change in treatment being clinically warranted
 - An adverse event
 - Any other significant reason identified by the Investigator.

If at any point during the study, the study device needs to be revised for any reason intraoperative data from the reoperation will be collected according to the Reoperation Case Report Form (CRF).

Reoperation cases will not be enrolled into the revision repair subject group if the subjects has been randomized previously into the ARCR augmented with REGENETEN arm. However subjects that have been randomized into the ARCR alone arm can be enrolled into the Revision Repair subject group.

CONFIDENTIAL AND PROPRIETARY

Study Protocol	Smith-Nephew
A Prospective, Multi-center, Randomized Controlled	Number:
Study to Evaluate the Safety and Efficacy of ARCR	REGENETEN.2020.01
augmented with REGENETEN™ Bioinductive Implant	Version: 2, 08 Dec 2021
System in Full-thickness Tears (large or massive) Repair versus ARCR alone	Page: 43 of 134

Following reoperation subjects shall continue to have follow-up visits in order to monitor the subject's health status only. Potential data following the reoperation will not be included as study data but presented separately as safety data.

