9.1.3 Operation – Visit 2 (Day 0)

- 1. Query subject regarding any changes in general health and the use of concomitant medications (e.g. oral or injected steroid use in last 4 weeks).
- 2. Confirm eligibility based on arthroscopic visualization of the tear and confirm size using a calibrated probe.
- 3. Assign the Randomization ID per randomization schedule. Screen Failure subjects should not be assigned randomization numbers, but their demographic information must be captured in the appropriate CRF with the reason for screen failure specified.
- 4. Commence operation as per the randomization schedule.
- 5. Collect operative and discharge data (including implant information) according to the CRF.
- 6. If any AEs, ADEs or DD are observed or reported, they must be recorded as instructed in Section 12 Adverse Events and Device Deficiencies.
- 7. Instruct the subject on proper postoperative care/procedures as per standard of care and/or Sponsor's recommendation given in section 6.2 Product Use.
- 8. Instruct the subject to document Opioid Use over the next 2 weeks on a daily basis.
- 9. Instruct the subject on follow-up procedures, including returning the treatment facility for follow-up at Visit 3 in 14 (± 5) days.

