10.2 ANALYSIS POPULATIONS

The following study populations and analysis sets will be defined.

- Full analysis set (FAS): following the Intention to Treat principle including all randomized patients who were recruited into the study and attended at least one post-surgery assessment. This analysis population includes all randomized patients in the groups to which they were randomly assigned, regardless of their adherence with the entry criteria, regardless of the treatment they actually received, and regardless of subsequent withdrawal from treatment or deviation from the protocol.
- Per protocol set (PP): including all patients in the full analysis set who have no significant protocol deviations and met the inclusion/exclusion criteria.
- Safety analysis set (SAF): including all patients who have received the study device.

CONFIDENTIAL AND PROPRIETARY

Study Protocol	Smith-Nephew
A Prospective, Multi-center, Randomized Controlled	Number:
Study to Evaluate the Safety and Efficacy of ARCR	REGENETEN.2020.01
augmented with REGENETEN™ Bioinductive Implant	Version: 2.0, 08 Dec
System in Full-thickness Tears (large or massive) Repair	2021
	Page: 71 of 134

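### Section 7.6 makes screen failure and enrolment depend on the treatment received, with no limit to the time before randomisation, so it conflicts with 9.1.2, 9.1.3 and the FAS in 10.2 and, on one reading, allows randomised subjects to be removed

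*Combined protocol and SAP*

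**What the plan says.** Five places in the protocol bear on who counts as a trial subject.

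- **7.6, enrolment.** A subject who consented, met the entry criteria and "received either ARCR augmented with REGENETEN or ARCR alone will be considered enrolled in the study".
- **7.6, screen failure.** "Subjects that provided informed consent but do not receive the study treatment for any reason will be considered as screen failure". No time limit is attached and 'study treatment' is not defined.
- **7.8.1, Withdrawal from Treatment.** The section opens: "Subjects may be withdrawn from having the study device implanted at a date close to surgery or during surgery for the following reasons"; the reasons are at the investigator's discretion and end with an open category.
- **9.1.2 and 9.1.3.** In 9.1.2, screen failure means failing the eligibility criteria. In 9.1.3 the Randomization ID is assigned at step 3, after arthroscopic confirmation, and the operation starts at step 4. It adds that "Screen Failure subjects should not be assigned randomization numbers".
- **10.2, Full analysis set.** The set is described as "including all randomized patients who were recruited into the study and attended at least one post-surgery assessment". It then keeps every randomised patient in the assigned arm, "regardless of their adherence with the entry criteria, regardless of the treatment they actually received". Withdrawal from treatment is also stated not to matter.

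Section 10.4.1 runs the primary analysis on the FAS and the per-protocol set. Section 8.2.2 says the study is not blinded.

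**The concern.** A rule that changes a subject's status after randomisation, according to what happened in the operating room, can undo the randomised comparison. Here the arm is known and the decision not to implant is discretionary. If a site or data manager codes such a subject as a screen failure, follow-up may stop and the subject may never reach the FAS. If the subjects removed have a higher retear risk than the rest of the device arm, the device-arm rate falls for a reason unrelated to the implant, and the test is biased towards superiority.

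The enrolment sentence raises a second case. A randomised subject later found not to have met an entry criterion is not enrolled under 7.6, yet 10.2 keeps that subject. This conflict does not depend on what 'study treatment' means.

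**Working it through.** **Step 1: apply each section to the same subject.** No plan figure is in dispute, so the first check is textual.

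| Randomised subject | 7.6, treatment = assigned device | 7.6, treatment = either procedure | 9.1.2 / 9.1.3 | 10.2 |
|---|---|---|---|---|
| Device arm, eligible, repaired without implant, attends follow-up | Screen failure | Enrolled | Not a screen failure: eligible and already numbered | In FAS, device arm |
| Either arm, treated as assigned, later found ineligible | Not enrolled | Not enrolled | Fails eligibility, yet already numbered | In FAS, assigned arm |
| Either arm, operation not done after the ID is assigned | Screen failure | Screen failure | Not a screen failure if eligible | As-randomised wording keeps the subject; the post-surgery assessment condition would probably not |

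The first row depends on the reading of 7.6; the second and third conflict on either reading.

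**Step 2: can 7.6 reach the analysis set?** The FAS wording asks that patients be randomised and also recruited. 'Recruited' is not defined. If it is taken to mean enrolled under 7.6, the 7.6 exclusions pass into the FAS. If it is taken as a loose synonym for entering the trial, they do not.

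**Step 3: what removal could do.** The documents give no non-implantation rate and no retear risk for such subjects, so both are assumed.

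Inputs: 130 per arm and a 30% control retear rate (section 11); two-sided 5% testing (10.1), hence 2.5% in the device's favour. Assume no true effect, so both arms retear at 30%. Remove a share k of the device arm with retear risk r.

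- Remaining device rate: p = (0.30 − k·r)/(1 − k), with n₁ = 130(1 − k) and n₂ = 130.
- Pooled rate: p̄ = (n₁p + n₂·0.30)/(n₁ + n₂).
- s₀ = √[p̄(1 − p̄)(1/n₁ + 1/n₂)] and s₁ = √[p(1 − p)/n₁ + 0.30·0.70/n₂].
- Error in the device's favour: Φ[(0.30 − p − 1.96·s₀)/s₁].

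Worked case, k = 5% and r = 60%: p = (0.30 − 0.03)/0.95 = 0.2842; n₁ = 123.5; p̄ = 0.2923; s₀ = 0.05715; s₁ = 0.05712; Φ[(0.0158 − 0.1120)/0.0571] = Φ(−1.685) = 4.6%.

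| Removed share k | Risk r | Device rate shown | One-sided error |
|---|---|---|---|
| 2%, 5% or 10% | 30% | 30.0% | 2.5% |
| 2% | 45% | 29.7% | 2.8% |
| 2% | 60% | 29.4% | 3.2% |
| 5% | 45% | 29.2% | 3.4% |
| 5% | 60% | 28.4% | 4.6% |
| 10% | 60% | 26.7% | 8.3% |

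A 2% share is 2 to 3 subjects (0.02 × 130 = 2.6), 5% is 6 to 7 (6.5) and 10% is 13. The calculation uses a single final look and ignores the interim analysis.

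**The case against.** The best defence is that 7.6 answers the main case itself. A device-arm subject who met the criteria and was repaired without the implant has had ARCR alone, which the enrolment sentence accepts. Read next to that sentence, 'study treatment' most naturally means either procedure. Section 7.6 also concerns status and does not say that data leave the analysis, while 10.2 states the as-randomised principle and covers withdrawal from treatment expressly. This stands as the more natural reading. It does not settle the matter: the term is undefined, the rule is open-ended as to reason, and 7.8.1 uses 'treatment' in its heading for having the device implanted. Nor does it resolve the ineligible-subject conflict.

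A reader might infer that only the device arm can lose subjects. That holds for the 7.8.1 route. It holds for non-receipt in general only if randomisation follows the repair, an order described in the amendment log (the flowchart itself is not reproduced). Under the order in 9.1.3, a subject in either arm whose operation is not done after the ID is assigned is also caught.

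A reader might also infer that implants would be dropped because of poor tissue or surgical difficulty. Section 7.8.1 does not say so, and exclusion criterion 19 makes contraindications under the instructions for use an eligibility matter. Elevated risk in removed subjects is therefore an assumption.

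**Conclusion.** The conflict is real and should be corrected. Section 7.6 contains two rules based on treatment received and on eligibility, neither confined to the time before randomisation, and they cannot be reconciled with 9.1.2, 9.1.3 and 10.2 as written. The documents do not show that subjects will be deleted; they leave a reading under which subjects could be.

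The size is unknown. Over the assumed scenarios the one-sided error runs from 2.5% (no inflation, when removed subjects have average risk) to 8.3% (10% of the device arm removed at twice the design control risk). At a 2% removal share it stays at or below 3.2%. These figures rest on assumed shares and risks, on removal from the device arm only, and on the exclusion actually reaching the FAS.

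**What to change.** In 7.6, replace the screen-failure sentence with: *Consented subjects who are not randomised (or, in the revision repair group, not treated) are screen failures. Every randomised subject is enrolled, followed and analysed in the FAS in the assigned arm, whether or not the implant is placed.* The bracket is needed because 8.2.1 says revision repair subjects are not randomised; without it, up to 40 planned subjects would become screen failures. Align the enrolment sentence in 7.6 with the new wording.

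In 10.2, delete the clause on recruitment from "including all randomized patients who were recruited into the study and attended at least one post-surgery assessment", so that FAS membership no longer depends on 7.6. Removing the post-surgery assessment condition is a separate question: it would bring in subjects without outcome data and is not needed here.

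The edit takes about three sentences and changes no treatment rule. Its cost is dilution of the estimated effect when implants are not placed. If implanted subjects retear at 15% and 5% of the arm is not implanted and retears at 30%, the as-randomised rate is 0.95 × 15% + 0.05 × 30% = 15.75%, and fixed-design power at 130 per arm is 78.4% instead of 82.9%. Larger shares or higher risks would cost more. The as-randomised principle in 10.2 already accepts that cost.
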